9.5. Follow-Up Phase

The follow-up phase is the interval between the EOT visit and the scheduled follow-up visit, which should occur 30 to 37 days following the EOT visit (or following the last dose of study drug if the EOT visit was not performed). If no follow-up visit is performed the follow-up phase is considered to be 30 days past the last dose of study drug. Reasonable efforts should be made to have the subject return for the follow-up visit, and report any AEs that may occur during this phase. The following procedures will be performed:

- Review concomitant medications.
- Record adverse events.
- Perform a targeted physical examination.

- Vital signs.
- Blood sampling for the following laboratory tests (see [Appendix 4](#)):
 - Serum chemistry tests
 - Hematology

9.6. **Unscheduled Visits**

Unscheduled visits for laboratory assessments may be conducted anytime at the Investigator's discretion. [REDACTED]

10. **STUDY ASSESSMENT PROCEDURES**

10.1. **Demographics and Medical History**

Demographic data and a complete medical and medication history will be collected at screening, after informed consent has been signed. Height and body weight measurements will be performed; body mass index will be calculated automatically in the eCRF. Complete transfusion history should be collected at the screening visit where possible, but must include at least 12 weeks prior to screening. All medical, medication and transfusion history will be recorded in the eCRF.

10.2. **Order of Assessments**

Multiple assessments are scheduled during the study visits. In order to standardize the visits, a suggested order of assessments is implied by the ordering of events in the description of study visits. Where feasible, vital signs and ECG measurements should be collected prior to blood draws. [REDACTED]

[REDACTED] Site staff should discuss the importance of the Subject Reminder Cards with the subject at the Day 1 visit so that the subject will be compliant with its return each visit. If the subject does not bring the reminder card, or it is blank, the site staff will discuss the prior dose timing with the subject, and will record the information in the subjects chart (site may use a blank reminder card for the specified visit).

10.3. **Safety Assessments**

10.3.1. **Adverse Events**

Adverse events will be monitored from the time the subject signs informed consent. Subjects will be instructed to report all AEs during the study and subjects will be assessed for the occurrence of AEs throughout the study. In order to avoid bias in eliciting AEs, subjects will be asked general, nonleading questions such as "How are you feeling?" All AEs (serious and nonserious) must be recorded on the source documents and case report forms regardless of the

assumption of a causal relationship with the study drug. The definition, reporting, and recording requirements for AEs are described in [Section 11](#).

10.3.2. Physical Examination

A comprehensive physical examination will be performed at the times indicated on the Table of Assessments ([Section 9](#)). The comprehensive physical examination will include the following organ or body system assessments: skin; head, eyes, ears, nose, and throat; thyroid; lungs; cardiovascular; abdomen (liver, spleen); extremities, lymph nodes, assessment for edema and/or ascites, measurement of weight and a brief neurological exam. Height will be measured at the Screening visit only. Physical exams must be performed by a medically qualified individual such as a licensed physician, Physician's Assistant or advanced Registered Nurse Practitioners as local law permits. Clinically significant findings will be recorded in the eCRF.

10.3.2.1. Targeted Physical

A targeted physical examination will be a symptom-directed evaluation. The targeted physical examination will include assessment(s) of the body systems or organs, as indicated by subject symptoms, AE, or other findings as determined by the Investigator or designee. The targeted physical examination should also include an assessment of the subject's weight.

10.3.3. Vital Signs

Vital sign measurements (blood pressure, heart rate, body temperature) will be collected on the days and times noted in the Table of Assessments ([Section 9](#)). Vital signs will be taken with the subject in the sitting position after 5 minutes of rest. Vital signs will be recorded in the eCRF.

10.3.4. Concomitant Medications

Concomitant medications will be collected on the days and times noted in the Table of Assessments ([Section 9](#)) and recorded in the eCRF.

10.3.5. Twelve-Lead Electrocardiograms

All 12-lead ECGs will be performed with the subject in a recumbent position after 5 minutes of rest.

The screening ECG will be interpreted by the Investigator or another appropriately trained individual at the site. If ECG abnormalities that are clinically meaningful are present, they will be recorded on the eCRF. Normal ECG findings or non-clinically meaningful abnormal ECG findings will not be recorded on the eCRF, other than data indicating the ECG was performed.

Twelve-lead ECGs may be conducted during the study at the Investigator's discretion. ECGs that are identified as abnormal and clinically meaningful compared to the Screening assessment should be reported as AEs. For such AEs, the findings of the abnormal ECGs and the corresponding baseline ECG findings must be reported in the eCRF, and copies of the abnormal tracings and corresponding baseline tracings will also be sent to the Sponsor and CRO for their records. For Sponsor:

██████████ MD
██████████ (FAX)

10.3.6. Laboratory Assessments

A central laboratory or as instructed in the lab manual will perform the clinical laboratory tests except for hematology and coagulation panel which will be performed by the local laboratory. Samples for serum chemistry, lipid panel, serology, [REDACTED] and serum pregnancy test will be prepared using standard procedures. All subjects will have samples of blood collected on the days and times noted in the Table of Laboratory Assessments (Table 4) for analysis of serum chemistry and hematology. Appendix 4 provides a complete list of laboratory tests that will be performed. Please refer to the laboratory manual for further details and specifications for sample handling, processing and shipping.

10.3.6.1. Hematology

Hematology assessments, including complete blood count (CBC) with manual differential will be performed by the local laboratory during study visits, and may be performed at this same laboratory, or at a local laboratory identified by the subject and investigator for laboratory-only visits as outlined in Table 4, and any other time additional hematology monitoring is deemed necessary. The investigator is responsible for obtaining the data from such local laboratories, as well as the normal lab ranges used by that laboratory. A standardized local laboratory range will be used in analysis of hematology lab data.

10.3.6.2. Chemistry

Chemistry labs will be analyzed by a central laboratory.

10.3.6.3. Pregnancy and Fertility Testing

Blood will be collected during screening for females of childbearing potential to conduct a pregnancy test. Females of non-childbearing potential are defined as women who are:

- At least 55 years of age with history of amenorrhea for 1 year OR
- Are surgically sterile for at least 3 months

Subsequently, pregnancy tests will be conducted only as medically indicated. A positive urine pregnancy test will be confirmed by a serum pregnancy test. Pregnancy status will be documented at each visit on the eCRF.

10.3.6.4. Serology

Serology labs will be analyzed by a central laboratory.

10.4. Efficacy Assessments

- **Imaging.** The primary measure of spleen size will be by MRI (or CT scan in applicable subjects). MRI of the upper and lower abdomen and pelvis will be performed at baseline and Week 24. MRI will be performed with a body coil because the objective is to measure organ volume, not to find very small lesions. MRIs will be read initially by local radiologists who will assess the scan for quality, and send all scans (MRI or CT) to the central imaging laboratory the same day, if at all possible. The scans from an individual subject will be read by a central reader. Spleen and liver volume will be obtained by outlining the circumference of the organ and

determining the volume using the validated technique of least squares. The MRI will not determine spleen length below the costal margin, as there are no validated approaches for determining this measurement. Procedure specific training for scanning and image capture will be provided by the Vendor.

[figure not shown]
[figure not shown]
[figure not shown]
MRI is the preferred method for obtaining spleen volume data. However, CT scans may be performed at the visits where MRI is designated if the subject is not a candidate for MRI (because of the presence of metal clips in the body, or because of claustrophobia, for example), or if MRI is not readily available. CT scans will be similarly processed by the same central laboratory as used for MRIs. Procedure specific training for scanning and image capture will be provided by the Vendor. NOTE: The same method (MRI versus CT) must be used for both visits for a given subject unless a new contraindication to the use of MRI (eg, pacemaker insertion) occurs.

[figure not shown]
[figure not shown]
- **Spleen length.** Spleen length will be assessed by manual palpation as outlined in [Table 3](#). Investigators will be provided with a soft centimeter ruler so that palpable spleen length is measured in centimeters and not in finger breadths. The edge of the spleen shall be determined by palpation, and measured in centimeters, using a soft ruler, from the costal margin to the point of greatest splenic protrusion. Spleen length must be recorded on the eCRF.

10.5. Symptom and Quality of Life Assessments

- **Symptom Diary.** Symptoms of MF will be assessed using a symptom diary (modified MFSAF v2.0 diary). Subjects will be issued a hand-held device on which to record answers to queries regarding MF symptoms. Symptoms assessed will include filling up quickly/early satiety, abdominal discomfort, abdominal pain, inactivity, night sweats, itching, and bone/muscle pain. The modified MFSAF v2.0 diary will be completed by subjects each night beginning at Day -7 (first day of Baseline), and continuing to the Week 24 visit (25 weeks total). Subjects will bring the device to the study site at Study visits on Day 1, Week 4, Week 8, Week 12 and Week 16, so that the device charging can be verified, and to download accumulated data. NOTE: subjects who will have overnight stays associated with their Study Visit must also bring their docking station so that their device can be fully charged at all times, and so they can complete the evening diary entries. The device will then be returned to the subject at these same visits for continued use each night. The subject will return the device and the docking station for the final time at the Week 24 visit so that the data can be archived. Detailed directions for the administration of the modified MFSAF v2.0 diary will be provided in a Reference Manual. Spanish translations of the modified MFSAF v2.0 diary will be available.
- Patient Global Impression of Change will be administered at each visit beginning with Week 4, and consists of a single question to which the subject responds with answer on a scale of 1 to 7. See [Appendix 5](#).

10.9. Other Study Procedures

10.9.1. Administration of Informed Consent Form

Valid informed consent must be obtained from the study subject prior to conducting any study-specific procedures. The granting of informed consent for participation in the study must be documented in writing, using an ICF that contains all the elements required by ICH E6 and describes the nature, scope, and possible consequences of the study in a form understandable to the study subject. Local and institutional guidelines for ICF content and administration must be followed, and a copy of the signed ICF must be provided to the study subject.

Subjects of childbearing potential must agree to take appropriate measures to avoid pregnancy or fathering a child in order to participate in the study ([Appendix 3](#)).

10.9.2. IVRS/IWRS Procedures

An IVRS system will be used to assign subject numbers and to dispense study drug. Procedures to be followed will be provided in an IVRS manual.

10.9.3. Study Drug Administration

Subjects will take their dose of ruxolitinib morning and evening, approximately 12 hours apart, and without regards to food.

10.9.4. Study Drug Dispensation

Site staff will contact an IVRS to obtain the subject study drug assignment. The investigator or designee will select the assigned bottles from their stock that correspond to the number provided by IVRS and dispense the medication. The investigator will enter the bottle numbers in the eCRF. At subsequent medication dispensing visits, the investigator or designee will follow the same procedures as described above. Full details will be provided in the IVRS manual.

10.9.5. Assessment of Study Drug Compliance

Compliance will be calculated by the Sponsor based on the drug accountability documented by the site staff and monitored by the Sponsor/designee (tablet counts). The objective is 100% compliance and investigators and their staff should evaluate compliance at each visit, and take appropriate steps to optimize compliance. For the purpose of subgroup analyses, subjects with at least 80% compliance over the total duration of dosing from the first day of dosing to the analysis of the study will be considered to be compliant.

10.9.6. Distribution of Subject Reminder Cards and Diaries

Subjects will be provided with subject reminder cards at each visit. The subject reminder cards will indicate the date/time of the next visit, and will also remind the subject when they should not take their morning dose of study drug, and when they should arrive for the visit after an overnight fast of at least 8 hours or since midnight. The reminder cards will have an area on which the date and time of the last dose taken prior to each study visit will be recorded by the subject, and to record time of last meal (certain visits only).

11. SAFETY MONITORING AND REPORTING

11.1. Adverse Events

11.1.1. Definitions and Reporting

An Adverse Event (AE) for the purposes of this protocol is defined as the appearance of (or worsening of any pre-existing) undesirable sign(s), symptom(s), or medical condition(s) that occur after a subject's signed informed consent has been obtained. Abnormal laboratory values or test results occurring after informed consent constitute AEs only if they induce clinical signs or symptoms, are considered clinically meaningful, require therapy (eg, hematologic abnormality that requires transfusion), or require changes in study drug(s).

Adverse Events that begin or worsen after informed consent should be recorded in the Adverse Events section of the CRF. Conditions that were already present at the time of informed consent should be recorded in the medical history section of the CRF. Adverse Event monitoring should be continued through the follow-up visit or for at least 30 days following the last dose of study treatment, whichever comes later. Adverse Events (including lab abnormalities that constitute AEs) should be described using a diagnosis whenever possible, rather than individual underlying signs and symptoms. When a clear diagnosis cannot be identified, each sign or symptom should be reported as a separate AE.

Adverse Events will be assessed according to the Common Terminology Criteria for Adverse Events (CTCAE) v4.03. If CTCAE grading is not used for a study, the severity of mild, moderate, severe, and life-threatening, or Grades 1 - 4, will be used. CTCAE Grade 5 (death) will not be used in this study; rather, information about deaths will be collected as an outcome of the event. The occurrence of AEs should be sought by non-directive questioning of the subject during the screening process after signing informed consent and at each visit during the study. Adverse Events may also be detected when they are volunteered by the subject during the screening process or between visits, or through physical examination, laboratory test, or other assessments. As far as possible, each AE should be evaluated to determine:

- The severity grade (CTCAE Grade 1-4)
- Reasonable possibility that AE is related to the study treatment: (no, yes)
- Reasonable possibility that AE is related to a study procedure: (no, yes)
- Start and end dates, unless unresolved at final exam
- Action taken with respect to study medication (none, dose adjusted, temporarily interrupted, permanently discontinued, unknown, not applicable)
- Outcome (not recovered/not resolved, recovered/resolved, recovering/resolving, recovered/resolved with sequelae, fatal, unknown)
- Whether it is serious, as per Serious Adverse Event (SAE) definition provided in [Section 11.3.1](#).

Unlike routine safety assessments, SAEs are monitored continuously and have special reporting requirements, see [Section 11.3.2](#).

All AEs should be treated appropriately. If a concomitant medication or non-drug therapy is given, this action should be recorded on the AE CRF as well as the Prior/Concomitant medications CRF.

Once an AE is detected, it should be followed until its resolution or until it is judged to be permanent; assessment should be made at each visit (or more frequently if necessary) of any changes in severity, the suspected relationship to the study medication, the interventions required to treat it, and the outcome.

Disease progression should not be regarded or reported as an AE itself, unless it is associated with a separate AE.

11.2. Laboratory Test Abnormalities

11.2.1. Definitions and Reporting

Laboratory abnormalities that constitute an AE in their own right (are considered clinically meaningful, induce clinical signs or symptoms, require concomitant therapy or require changes in study treatment), should be recorded on the AE CRF. Whenever possible, a diagnosis, rather than a symptom should be provided (eg, anemia instead of low hemoglobin). Laboratory abnormalities that meet the criteria for AEs should be followed until they have returned to normal or an adequate explanation of the abnormality is found. When an abnormal laboratory or test result corresponds to a sign or symptom of a previously reported AE, it is not necessary to separately record the lab/test result as an additional event.

Laboratory abnormalities that do not meet the definition of an AE should not be reported as AEs. A Grade 3 or 4 (severe) event, as per CTCAE, does not automatically indicate a SAE unless it meets the definition of serious, as defined below, and/or as per investigator's discretion. A dose hold or medication for the lab abnormality may be required by the protocol in [Section 8.6](#) and should not contribute to the designation of a laboratory test abnormality as a SAE.

11.3. Serious Adverse Events

11.3.1. Definitions

Serious Adverse Event (SAE) is defined as one of the following:

- Is fatal or life-threatening (ie, immediate risk of dying)
- Results in persistent or significant disability/incapacity
- Constitutes a congenital anomaly or birth defect
- Is clinically meaningful, (ie, defined as an event that jeopardizes the subject or requires potential medical or surgical intervention to prevent 1 of the outcomes listed above). Considered meaningful by the Investigator as an important medical event that may not result in death, be life-threatening, or require hospitalization, but may be considered a SAE when, based upon appropriate medical judgment, it may jeopardize the subject or may require medical or surgical intervention to prevent 1 of the outcomes listed in this definition.

- Requires inpatient hospitalization or prolongation of existing hospitalization, unless hospitalization is due to:
 - Routine treatment or monitoring of the studied indication, not associated with any deterioration in condition.
 - Elective or pre-planned treatment for a pre-existing condition that is unrelated to the indication under study and has not worsened since signing the informed consent.
 - Treatment on an emergency outpatient basis for an event not fulfilling any of the definitions of a SAE given above and not resulting in hospital admission.
 - Social reasons and respite care, in the absence of any deterioration in the subject's general condition.
 - Any SAEs that are expected due to the condition being treated, including if the SAE is a primary outcome measure, and whether there has been a clear agreement with regulators not to consider these as SAEs, provided the information is collected elsewhere.

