4. INTRODUCTION

The four classic myeloproliferative neoplasms (MPNs) include chronic myelogenous leukemia (CML), polycythemia vera (PV), essential thrombocythemia (ET) and primary myelofibrosis (PMF). Myelofibrosis (MF) can present as a de novo disorder (PMF) or evolve secondarily from previous PV or ET (post-PV-MF or post ET-MF). Regardless of whether MF is a primary or secondary disorder, it is characterized by a clonal stem cell proliferation associated with production of elevated serum levels of multiple inflammatory and proangiogenic cytokines, a characteristic bone marrow stromal pattern that includes varying degrees of collagen fibrosis, osteosclerosis and angiogenesis and a peripheral blood smear showing a leukoerythroblastic pattern with varying degrees of circulating progenitor cells. Clinically, MF is characterized by progressive anemia, leukopenia or leukocytosis, thrombocytopenia or thrombocytopenia and multi-organ extramedullary hematopoiesis most prominently involving the liver and spleen. Patients may experience severe constitutional symptoms, sequelae of massive splenomegaly (pain, limitations of movement, early satiety and shortness of breath, hepatic obstruction, and splenic infarction), a hypermetabolic state with cachexia, progressive hematopoietic failure, progression to leukemia, and premature death.

The median age at diagnosis is approximately 60 to 65 years. The incidence of PMF has been estimated at 1.5 cases per 100,000 people. Survival in MF varies with the presence or absence of specific risk factors. A prognostic scoring system based on a time-dependent risk evaluation has been developed: the Dynamic International Prognostic Scoring System (DIPSS) for PMF ([Passamonti et al 2010](#)), age of greater than 65 years, presence of constitutional symptoms, anemia (Hemoglobin less than 100 g/L), leukocytosis (white blood cell count (WBC) greater than $25 \times 10^9/L$), and a circulating blast percentage of 1% or higher were assessed for their impact on survival when analyzed as time-dependent covariates in a multivariate Cox proportional hazard model. The approach showed that acquisition of anemia over time affects survival with a hazard ratio roughly double that of other parameters; anemia was therefore assigned a score of 2, while the other 4 factors were assigned scores of 1. Four risk categories with non-overlapping survival curves have been described:

| Total Risk Score | Risk Category | Median Survival (months) |

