4.3. Potential Risks and Benefits of the Treatment Regimen

4.3.1. Potential Risks

No specific findings in nonclinical repeat dose toxicity studies identify clinical risks other than noting that consequences of immunosuppression may occur. Hypotension and increases in heart rate were noted at a high dose in a cardiovascular preclinical study. However, these findings have not been recapitulated in a clinical setting.

The primary clinical risks with ruxolitinib treatment are the potential sequelae of decreased hematopoietic proliferation secondary to the inhibition of growth factor pathways by JAK2 inhibition. Dose-dependent, reversible thrombocytopenia has been observed in subjects with MF and represents the DLT. The risk of spontaneous hemorrhage in patients as a result of thrombocytopenia generally does not become manifest until platelet counts fall below $10 \times 10^9/L$ (Slichter 2004); platelet counts below $25 \times 10^9/L$ (Grade 4) were not observed in any subjects initiating ruxolitinib at starting doses of 10 mg bid or 15 mg bid in the ongoing phase 1/2 study. In the current study, dosing must be interrupted for platelet count below $25 \times 10^9/L$, or for Grade 2 or higher hemorrhage events that are assessed as at least possibly related to ruxolitinib therapy.

Anemia and, less frequently, neutropenia have also been observed in patients with MF treated with ruxolitinib. Increased rates of infection and anemia are potential risks of myelosuppression, and there are multiple sequelae of anemia including the burden and risks of transfusion. A few subjects have had an apparent worsening of their pre-morbid disease symptoms following rapid cessation of ruxolitinib therapy and a gradual tapering and use of steroids in fragile subjects may be considered when stopping ruxolitinib therapy.

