8.6.6. Optional Dose Tapering Strategy

In ongoing clinical studies with ruxolitinib, exacerbation of underlying cardiopulmonary disease and return of MF symptoms has been occasionally observed in subjects after drug discontinuation. When a decision is made to permanently discontinue ruxolitinib therapy for reasons other than low platelet counts or ANC levels, tapering of ruxolitinib dosage may be considered, based on evaluation of the condition of the subject, current dose regimen and the clinical judgment of the investigator. Doses of ruxolitinib may be very slowly lowered until the subject is completely off drug. If medically indicated, doses of ruxolitinib may be temporarily restarted after they have been discontinued. If considered to be medically necessary, the investigator may use any treatment to manage withdrawal from ruxolitinib including, but not limited to, the management of events which may be secondary to discontinuation, and interruption or reduction of dose administered of ruxolitinib. Short-term courses of high-dose corticosteroids, equivalent to doses of > 10 mg/day of prednisolone have been used to moderate the withdrawal of ruxolitinib and may be considered as part of a tapering strategy. Corticosteroids may be started prior to, or concurrent with, ruxolitinib tapering in anticipation of the possibility of occurrence of withdrawal symptoms. When a decision has been made to discontinue the subject with utilization of a tapering strategy, regardless of the use of concomitant medications, safety data will continue to be assessed in accordance with the protocol. An end of study and subsequent follow-up visit must be scheduled.

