11.3.2. Reporting

To ensure subject safety, every SAE, regardless of suspected causality, occurring after the subject has signed the informed consent form (ICF) and until (at least) the Follow-up Visit or 30 days after the subject has stopped study treatment (whichever comes later) must be reported to the Sponsor or designee within 24 hours of learning of its occurrence. Any SAEs experienced after this period of at least 30 days should only be reported to the Sponsor, or designee, if the Investigator suspects a causal relationship to the study medication. Recurrent episodes, complications, or progression of the initial SAE must be reported as the follow-up to the original episode within 24 hours of the Investigator receiving the follow-up information. An SAE occurring at a different time interval or otherwise considered completely unrelated to a previously reported one should be reported separately as a new event. Serious AE collection begins after the subject has signed the ICF. If a subject experiences an SAE after signing the ICF, but prior to receiving study medication, the event will **not** be collected unless the Investigator feels the event may have been caused by a protocol procedure. Previously planned (prior to signing the ICF) surgeries should not be reported as SAEs unless the underlying medical condition worsens over the course of the study.

Information about all SAEs is collected and recorded on the Serious Adverse Event Report Form. The Investigator must assess and record the relationship of each SAE to each specific study medication (if there is more than 1), complete the SAE Report Form in English, and send the completed, signed form by fax within 24 hours to the Sponsor (or designee). The investigator must assess if there is a Reasonable possibility that the SAE is related to the study treatment: no (unrelated), yes (related).

SAEs related to unblinded comparator drugs or concomitant medications/drug delivery systems are reported directly to the manufacturers of those drugs/devices in accordance with the package insert.

The telephone and facsimile number of the Sponsor's contact persons, specific to the study, are listed in the investigator folder provided to each site. The original copy of the SAE Report Form and the fax confirmation sheet must be kept with the case report form documentation at the study site.

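### The open-ended exception for disease-expected hospitalizations in Protocol 11.3.1 can understate the SAE tables and 24-hour SAE reporting, and can do so differently by site

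*Protocol*

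**What the plan says.** Protocol 11.3.1 gives hospitalization as one seriousness criterion: "Requires inpatient hospitalization or prolongation of existing hospitalization, unless hospitalization is due to" one of several listed reasons. The last reason is "Any SAEs that are expected due to the condition being treated, including if the SAE is a primary outcome measure", which continues "whether there has been a clear agreement with regulators not to consider these as SAEs, provided the information is collected elsewhere".

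Protocol 11.3.2 requires that "every SAE, regardless of suspected causality" be reported to the sponsor or its designee within 24 hours of the site learning of it.

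Three other sections bear on what is expected from the condition:

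- Section 4 (Introduction): "Clinically, MF is characterized by progressive anemia, leukopenia or leukocytosis". The same description goes on to thrombocytopenia, constitutional symptoms and hematopoietic failure.
- Section 4.3.1 (Potential Risks): thrombocytopenia is the dose-limiting toxicity, and anemia and neutropenia have been seen on drug. It adds: "Increased rates of infection and anemia are potential risks of myelosuppression".
- Section 8.6.6 (Optional Dose Tapering Strategy): "exacerbation of underlying cardiopulmonary disease and return of MF symptoms has been occasionally observed in subjects after drug discontinuation".

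Safety and tolerability is a primary objective (Protocol 5.1), and the study is single arm (8.3).

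**The concern.** The exception turns on a judgment that this trial cannot check. For anemia, thrombocytopenia or returning MF symptoms, the investigator must decide whether the admission was to be expected from the disease. The protocol gives no list to decide by, and no comparator arm shows the background rate. Two sites with the same patient could classify the admission differently, and both could say that they followed the text.

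The outputs at stake are those that depend on the serious label: the SAE count in the SAP 8.1 high-level summary, SAEs by organ class and preferred term, the SAE listing, 24-hour reporting under Protocol 11.3.2, and any later handling as a suspected unexpected serious adverse reaction, which requires seriousness. SAP 8.1 also tabulates non-serious treatment-emergent AEs. An exempted admission would move into that table, where a reader would take it for a milder event.

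**Working it through.** The plan states no figure on this point, so the check is mainly a comparison of sections.

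**1. Does anything bound the exception?** Two conditions follow the exempted events.

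- The regulator agreement is introduced by *whether*, so the sentence does not clearly require that an agreement exist. The protocol cites none.
- The information must be collected elsewhere, but no place is named. The AE attributes listed in 11.1.1 are severity, relatedness to drug and to procedure, dates, action taken, outcome and seriousness. Hospitalization is not among them, and the seriousness item points back to 11.3.1.

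**2. Do disease features and drug effects overlap?**

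| Event | Feature of MF (section 4) | Effect of drug or of stopping it |
|---|---|---|
| Anemia | Yes | Yes (4.3.1) |
| Thrombocytopenia | Yes | Yes, dose-limiting (4.3.1) |
| MF symptoms | Yes | Return after stopping (8.6.6) |
| Neutropenia | Indirectly, through leukopenia | Yes (4.3.1) |
| Infection | Not named in the description of MF | Yes (4.3.1) |
| Hemorrhage | Not named in the description of MF | Monitored as a risk (11.7.2) |

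The overlap is direct for the first three rows only.

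**3. Which seriousness routes stay open?** The exception attaches to the hospitalization criterion alone. Fatal or life-threatening events, disabling events and important medical events remain SAEs. The last route rests on investigator judgment. Protocol 11.2.1 adds that a Grade 3 or 4 event is not automatically serious, and that a protocol-required hold or medication for a laboratory abnormality should not count toward SAE status.

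**4. Which other reporting is independent of SAE status?** The 24-hour fax in Protocol 11.7.2 covers Grade 4 thrombocytopenia and Grade 3 or 4 hemorrhage. It does not cover hospitalized anemia or returning MF symptoms.

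**5. Which analyses are unaffected?** All AEs, serious or not, are recorded (Protocol 10.3.1). SAP 8.1 tabulates all TEAEs and Grade 3 or 4 TEAEs. It takes Grade 4 thrombocytopenia and Grade 4 anemia from laboratory data, and Grade 2 or higher hemorrhage from a standardized MedDRA query. For example, the interim Grade 4 platelet figure in Protocol 4.1.5, 8/50 = 16%, comes from laboratory values, so the exception cannot lower it.

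**6. How large could the effect on the SAE count be?** The documents give no SAE rate. As an illustration on assumed inputs, let *p* be the true share of 150 subjects with an SAE and *q* the share of those whose SAEs qualify only through an exempted hospitalization. The count shown is 150 × *p* × (1 − *q*).

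| Assumed *p* | True count | Shown at *q* = 10% | Shown at *q* = 50% |
|---|---|---|---|
| 20% | 30 | 27 (18%) | 15 (10%) |
| 30% | 45 | 40.5 (27%) | 22.5 (15%) |
| 40% | 60 | 54 (36%) | 30 (20%) |

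The shortfall *p* × *q* runs from 2 to 20 percentage points over this range. It assumes that every eligible admission is exempted, so each cell is an upper bound for its inputs.

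**The case against.** The strongest reply is that the bullet, read to its end, carries two cumulative conditions. Without a regulator agreement it is never triggered, and with one the information must still be captured elsewhere. An agreement may exist outside these documents. That reading is possible, but the wording does not require it, and a site has nothing in the protocol by which to tell whether the conditions are met.

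The second reply is that little is lost even when the exception is used, because the events remain AEs and the named safety endpoints do not use the serious label. This stands, and it limits the point. A reader might infer that serious drug effects would disappear from the safety result. The documents do not support that: the TEAE, graded, laboratory-based and query-based outputs are unaffected. Complete loss would need a further step, in which the site also calls the event disease progression, which 11.1.1 says is not itself an AE unless associated with a separate one.

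Three further inferences also fail:

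- **That the DMC loses 24-hour notice.** SAEs go to the sponsor or its designee. The DMC sees safety data at its reviews (Protocol 11.7, SAP 5.1), including AE and laboratory data.
- **That 11.3.1 contradicts 11.3.2.** The narrower definition limits what 11.3.2 covers, but the two sections are consistent.
- **That admissions for infection or bleeding are plainly exempt.** Section 4 does not name either in its clinical description of MF, so their exposure is indirect.

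**Conclusion.** The point holds for SAE classification. As written, the exception lets sites treat admissions for anemia, thrombocytopenia or returning MF symptoms as non-serious when no other seriousness criterion is met. SAE counts, SAE tables and 24-hour reporting to the sponsor can therefore be too low, by an amount that depends on each site's reading. With no control arm, the size of that understatement cannot be recovered from the SAE data.

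The amount is unknown. The illustrative range of 2 to 20 percentage points rests wholly on assumed rates and concerns the SAE row only. The Grade 4 thrombocytopenia and Grade 2 or higher hemorrhage endpoints are not affected. The correction is worth making because safety is a primary objective and the change is small. It does not call the trial's main safety analyses into question.

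**What to change.** Delete the last bullet of the hospitalization exceptions in Protocol 11.3.1.

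If the sponsor holds a regulator agreement, replace the bullet with text that:

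- cites the agreement and makes it an explicit condition;
- lists the exact exempt terms;
- names the form or dataset in which exempt hospitalizations are recorded;
- states that cytopenias, hemorrhage, infection and events after interruption or stopping of ruxolitinib are not exempt when a seriousness criterion is met.

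The cost is one edit, a notice to sites and some additional SAE forms for disease-related admissions. No SAP analysis has to change.
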